## 1.0 ADMINISTRATIVE INFORMATION, Part A

Title	Using BCG vaccine to enhance non-specific protection of senior citizens during the COVID-19 pandemic. A randomized clinical trial (BCG-DENMARK-SENIOR).
Trial registration	EudraCT number 2020-003904-15
SAP version and date	2.0, 08-06-2023
Protocol version and date	4.3, 31-01-2022
SAP contributors	[name] (PI) [name] (Sponsor) [name] (Data analyst) [name] (Statistician)
Sponsor	[name] University of Southern Denmark, Department of Clinical Research and Bandim Health Project
Primary investigator	[name] University of Southern Denmark, Department of Clinical Research and Bandim Health Project
Trial statistician	[name] The Arctic University of Norway, Tromsø Department of Community medicine
SAP revision history	
Revision 08-06-2023:
 
Updated section 6.0 and 7.0:
 
 
1. The composite outcome will include all infectious disease hospital contacts.
 
2. Data does not support analysis of COVID-19 severity, this outcome has been removed.
 
3. New secondary outcome has been added: All-cause hospitalization.
 

Date of approval	

## 2.0 INTRODUCTION

### Background

Worldwide, the population of persons > 60 years of age is growing because of advances in average life expectancy, especially in high income countries. Due to age related decline in immune function, so called immunosenescence, the elderly are at higher risk of infectious diseases. Severe infections are more common in the elderly, and they are more likely to be hospitalized due to complications related to infectious diseases. During the COVID-19 pandemic, it has become clear that elderly people are particularly susceptible to severe COVID-19. Strategies to strengthen senior citizens' immune system are urgently warranted.

The Bacille Calmette Guérin (BCG) vaccine was developed for tuberculosis prevention, but there is increasing evidence that it also has beneficial heterologous "non-specific" effects on the immune system. Prior studies have shown that BCG vaccination strengthens the innate immune system resulting in increased activity against non-related infections. BCG vaccination may strengthen the immune system of senior citizens and may (partially) protect against getting infected and/or experiencing severe morbidity due to infections in general and SARS-CoV-2 in particular.

We hypothesize that BCG vaccination can reduce the risk of COVID-19 and other infections among senior citizens during the COVID-19 pandemic. A randomized controlled trial provides the highest validity for this research question.

### Objectives and hypothesis

Primary objective: To reduce senior citizens' risk of acute infection during the COVID-19 pandemic.

Secondary objectives: To reduce senior citizens' risk of SARS-CoV-2 infection during the COVID-19 pandemic and to reduce self-reported respiratory illness in general during the COVID-19 pandemic.

The hypothesis is that BCG vaccination of seniors will reduce the risk of acute infection by 25% over a period of 12 months.

## 3.0 STUDY METHODS

### Trial design

A single-blinded, placebo controlled randomized clinical trial. Participants are randomized 1:1 to BCG or placebo and will be followed for 12 months post-randomization with respect to illness, medical contacts, use of antibiotics, hospitalization, and death. The follow-up takes place both through self-reporting and through the Danish National Registers. The participants will receive an electronic questionnaire biweekly with questions about illness, medical contacts, other vaccinations, and side effects.

People  $\geq 65$  years of age are eligible for participation.

### **Randomization**

Randomization takes place at baseline after informed consent is given. The randomization is done in varying blocks of 6-8, stratified by sex and age group (65-74; 75+) using REDCap electronic data capture tools hosted at the Region of Southern Denmark.

### **Sample size**

With an expected incidence of “acute infection” of 20% we will be able to show a 25% reduction in the risk of acute infection in the intervention group compared to the placebo group by including a total of 1890 individuals: 945 individuals in each group. Since the primary outcome data to a large extent are obtained via national registers, we anticipate limited loss of power due to loss to follow-up. We therefore aimed to enroll 1900 participants.

Due to the pandemic and varying infectious disease precautions, recruitment took longer than anticipated, and we ended up recruiting a total of 1706 participants (90% of the anticipated sample size) between September 2020 and December 2021.

### **Timing of final analyses and outcome assessments**

All outcomes are analyzed after end of trial.

## **4.0 STATISTICAL PRINCIPLES**

### **Levels of confidence and p-values**

A double-sided p-value of  $< 0.05$  will be considered statistically significant. 95% confidence intervals will be provided.

### **Protocol violations**

Protocol deviations and exclusions will be reported for each treatment arm.

## 5.0 STUDY POPULATION

### Screening data

Around 35,000 elderly > 65 years live in Odense at the time of recruitment. The study is based on voluntary participation open to all eligible persons on their own initiative. Interested persons are screened for participation after they have received oral and written information and declared their continued interest for participation. We keep a list of persons screened for participation and reasons for not being included/being excluded.

### Recruitment

Recruitment, enrolment, and follow-up with collection of biological material is conducted at activity houses for senior citizens run by the Municipality of Odense. The project is presented at special arrangements at these houses and advertised in local media and via posters in relevant public places.

### Exclusion/loss to follow-up

Participants who are excluded after randomization or lost to follow up are not replaced. Participants are under follow-up for 12 months post-randomization or until they withdraw their consent, migrate to another country, or die.

### Baseline characteristics, study population

Continuous baseline characteristics will be reported as mean with standard deviation or median with inter-quartile range, as appropriate. Categorical baseline characteristics will be reported as count and percentage. No statistical testing for baseline characteristics will be performed.

## 6.0 DESCRIPTION OF OUTCOMES AND VARIABLES

### Primary outcome

The primary outcome is a composite outcome: acute infection identified either by a doctor, by antibiotics use, by hospitalization, or by death due to infection. All subcomponents will also be presented separately.

Information on hospitalizations, deaths, and antibiotics use is retrieved from national health registers: The Danish National Patient Register, The Central Person Register, and The National Prescription Register. All hospital contacts due to acute infection will be included, regardless of duration of the contact. An acute infection event identified by a doctor is defined as newly onset infectious illness that has prompted the participant to seek medical attention from general practitioner (GP) or on-call doctor and is based on self-reporting. Participants are asked in the questionnaires, if they have needed to see their GP or an on-call doctor due to newly onset illness during the past 14 days (yes/no). Thus, participants can only have one such event per survey period (14 days). For all outcomes, a honeymoon period of 14 days will be used to define new events.

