**Table 4 Adverse Events (AE) and Serious Adverse Events (SAE)**

Endpoint	BCG	Placebo
	Number (%) [M/F]	Number (%) [M/F]
Any SAE		
Hospitalization for any reason		
Death due to any reason		
Adverse events (AE):		
Injection site reaction		
Minor abscess/wound		
Severe local reaction (abscess)		
Fever		
Fatigue		
Headache		
Lymphadenitis		
Serious Adverse Events (SAE):		
Blood or lymphatic disorder		
Cardiac disorders		
Endocrine disorders		
Gastrointestinal disorders		
Infection		
Musculoskeletal and connective tissue disorders		
Nervous system disorders		
Respiratory disorders		

Urological and gynecological disorders		
Unknown/other		
Outcome SAE:		
Life threatening		
Required/prolonged hospitalization		
Resulted in death		

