### **Sample size**

We aim to include 75 participants in each group, 300 in total. With an anticipated seroconversion rate of 50% in the control group, we should be able to show a 30% increase in seroconversion rate associated with BCG vaccine with 80% power and an alpha of 0.05, anticipating 10% loss to follow-up.

All participants are followed for clinical symptoms for six months. With this sample size, we will only be able to show differences in clinical symptoms if such differences are pronounced.

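### The Part A primary composite does not separate treated injection-site abscess/wound or lymphadenitis from acute infection, and no sensitivity analysis shows the effect

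*SAP*

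**What the plan says.** SAP Part A, section 6.0, defines the primary outcome as "acute infection identified either by a doctor, by antibiotics use, by hospitalization, or by death due to infection". Its parts are fixed as follows:

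- **Antibiotics:** the component row of the variables table asks only for treatment during follow-up and names no indication. The data come from the prescription register.
- **Hospital:** every contact due to acute infection counts, however short.
- **Doctor:** a self-reported visit to a GP or on-call doctor for a new infectious illness.
- **Event spacing:** a 14-day gap decides when an event is new. It does not exclude any type of event.

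Follow-up runs for 12 months from randomization (section 5.0), and time since inclusion is the time scale (section 7.0). The period just after the injection is therefore fully at risk.

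In section 8.0, Table 4 has adverse-event rows for minor abscess or wound, for lymphadenitis, and a row that starts "Severe local reaction (abscess". Infection is a separate row among the serious adverse events.

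The title states the aim as non-specific protection. Section 2.0 adds: "The hypothesis is that BCG vaccination of seniors will reduce the risk of acute infection by 25% over a period of 12 months".

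**The concern.** Safety reporting keeps local vaccine reactions apart from infection. The efficacy endpoint does not. A participant treated with antibiotics for an abscess at the injection site enters Table 4 as a reaction and the primary analysis as an acute infection.

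This is not the ordinary noise of a broad endpoint. Non-specific misclassification falls on both arms, whereas a reaction caused by the study vaccine depends on allocation and can only work against BCG. Limiting antibiotics to infectious indications would not remove it, because an abscess would usually pass that filter.

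What is at stake is how a null or adverse primary result is read. Without a separate analysis, the reader cannot tell absent protection against unrelated infections from protection partly offset by counted site reactions.

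**Working it through.** **Inputs**

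- Placebo risk 20% and a 25% relative reduction, so 15% under BCG (section 3.0, Sample size).
- Two-sided alpha 0.05 (section 4.0, "A double-sided p-value of" below 0.05).
- Power is not stated for Part A. I assume 80%; Part B is planned "with 80% power and an alpha of 0.05".
- Planned 945 per arm; recruited 1706 in total, so 1706/2 = 853 per arm.
- h, the share of BCG recipients with a site reaction or lymphadenitis that scores a primary event, is not in the document. I assume 0.25% to 2%, with zero in the placebo arm.

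**Step 1: reproduce the plan's figure**

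The plan states its size as "by including a total of 1890 individuals: 945 individuals in each group". The two-proportion formula without continuity correction gives

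n = [1.96 × √(2 × 0.175 × 0.825) + 0.8416 × √(0.20 × 0.80 + 0.15 × 0.85)]² / 0.05² = 906 per arm (rounded up).

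With the continuity correction,

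n' = (n/4) × [1 + √(1 + 4/(n × 0.05))]² = 945 per arm, or 1890 in total.

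The match is exact, so 20% v 15% with 80% power is the right base.

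**Step 2: add counted reactions to the BCG arm**

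If reactions are independent of other infections, the BCG-arm risk is p = 1 − 0.85 × (1 − h), and

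RR = p / 0.20 = 0.75 + 4.25h.

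| h (assumed) | BCG recipients of 853 | BCG-arm risk | RR | Apparent reduction | Power at 853 per arm |
|---|---|---|---|---|---|
| 0 | 0 | 15.00% | 0.750 | 25.0% | 77.6% |
| 0.25% | about 2 | 15.21% | 0.761 | 23.9% | 73.8% |
| 0.5% | about 4 | 15.42% | 0.771 | 22.9% | 69.7% |
| 1% | about 9 | 15.85% | 0.792 | 20.8% | 60.8% |
| 2% | about 17 | 16.70% | 0.835 | 16.5% | 42.1% |

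Power is the uncorrected normal approximation. At 2% the share of the planned reduction that is lost is (25.0 − 16.5)/25.0 = 34%. At 0.25% it is (25.0 − 23.9)/25.0, about 4%.

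**Step 3: no true effect on other infections**

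RR = [1 − 0.80 × (1 − h)] / 0.20 = 1 + 4h. This is 1.01 at 0.25% and 1.08 at 2%, an appearance of slight harm.

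**Step 4: how far this carries to the planned model**

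The primary analysis counts recurrent events, so a binary risk only approximates it. On a rate scale, with the rates implied by 20% and 15%, the ratio moves from −ln(0.85)/−ln(0.80) = 0.728 to (0.1625 + 0.02)/0.2231 = 0.818 at h = 2%. A higher background rate of repeat infections would dilute the shift. A slow-healing reaction treated again after more than 14 days could count twice and enlarge it.

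**The case against.** Several stronger readings are tempting, and the SAP does not support them.

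- **All treated reactions count by any route.** A reader might infer that every abscess, wound or swollen node that leads to a doctor or hospital contact is a primary event. Those components require an infectious cause, and the SAP does not say how a vaccine reaction or reactive node would be classed. The questionnaire also treats side effects as a topic of their own. Counting follows plainly only through antibiotics. Even there, the composite's row in the variables table can be read as attaching an infectious cause to all four parts, but the antibiotic row sets no such limit and no rule for applying one is given.
- **The reactions belong to one arm.** This may be inferred from Table 4's list, but the SAP does not state it. The table is an empty shell with a column for each arm.
- **A large share of the effect would be hidden.** Adding 2% directly to 15% gives 17%/20% = 0.85, a loss of 40% of the planned reduction. That ignores overlap with other infections and rests on an assumed rate. At 0.25% the shift is negligible.
- **The events should be removed from the primary outcome.** The hypothesis concerns acute infection, analysed by intention to treat, so a net effect on all infections is defensible. Site reactions hint at the arm, so case-by-case attribution would not be truly blind. Deleting coincident events would drop true infections mainly from the BCG arm and favour BCG.

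It is also fair that the bias cannot create a false claim of benefit, that the components are shown separately, and that the protocol, not shown here, may hold classification rules. These points limit the size of the concern and decide the form of the fix. They do not supply the missing separation in section 6.0 or 7.0.

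**Conclusion.** The point holds in a limited form. The SAP counts antibiotic courses without regard to indication, together with doctor and hospital contacts classed as infectious. It does not distinguish injection-site abscess/wound or lymphadenitis, which it expects to tabulate as adverse events. If these occur mainly after BCG, the primary hazard ratio is pulled against BCG for a reason unrelated to non-specific protection.

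The size cannot be fixed from the document. Over an assumed 0.25% to 2% of BCG recipients, the risk ratio goes from 0.75 to between 0.76 and 0.835. This rests on the planned 20% v 15%, independence from other infections, no such events under placebo, and a binary approximation. The true shift may be small. The gap calls for one added analysis and gives no ground for redefining the endpoint.

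**What to change.** Keep the composite as the primary analysis. Add to Part A, section 7.0, a sensitivity analysis that repeats the primary model after excluding primary events that match a recorded adverse event of injection-site abscess/wound or lymphadenitis in the same participant.

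- Define the match by a fixed date window, set before unblinding and applied mechanically without the allocation code, with no case-by-case judgement. If the code is already broken, label the analysis post hoc.
- Remove matched events before applying the 14-day rule, so that an excluded event does not mask a later infection.
- Report the number of events excluded per arm, by component.

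The cost is a short paragraph, one further model run and a match to records already collected, since the biweekly questionnaires ask about side effects. The SAP does not say how precisely non-serious adverse events are dated, so the window may have to follow the 14-day survey period. The downside is that some coincident true infections may be dropped, mainly in the BCG arm. That is why this should remain a sensitivity analysis.

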## Variables

Variable	Definition	Type	Scale
Primary outcome:			
Acute infection	Death, hospitalization, antibiotic treatment, or visit to GP due to newly onset infectious disease. Composite outcome.	Categorical, binary	0,1
Death due to infection	Death due to infectious disease.	Categorical, binary	0,1
Hospitalization for infection	Hospital contact due to infectious disease.	Categorical, binary	0,1
Antibiotic treatment	Antibiotic treatment during follow-up.	Categorical, binary	0,1
Doctor diagnosed infection	Infection identified by GP or on-call doctor.	Categorical, binary	0,1
Secondary outcomes:			
Self-reported respiratory infection	Reported respiratory symptoms or disease compatible with respiratory infection.	Categorical, binary	0,1
Verified CoV  infection (first event)	Positive SARS-CoV-2 test.	Categorical, binary	0,1
All-cause hospitalization	Admission to hospital > 24 hours (first event).	Categorical. binary	0, 1

 SARS-CoV-2 infection.

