### **Secondary outcomes**

*Self-reported infections:*

Infections are identified through information given by the participants in the electronic follow-up questionnaires, where they are asked to describe disease episodes every 14 days. They are asked if they have been ill, and then asked to cross off their symptoms on a list. Furthermore, we ask them to provide the most likely cause for their illness. Disease episodes are characterized as infections if participants report symptoms compatible with an infectious disease or they report an infectious disease diagnose as the cause of their illness. Criteria for self-reported infection:

- Having one or more of the following symptoms: fever, cough, sore throat, runny nose/nasal congestion (common cold symptoms), loss of smell or taste sense, vomiting, or diarrhea with or without general symptoms such as headache, myalgia, dysarthria, or fatigue.
- Having dyspnea AND fever with or without general symptoms such as headache, myalgia, dysarthria, or fatigue.
- Having described an infectious disease as the self-estimated cause of illness. This is a free-text field and participants answers will be classified as infectious disease or not by medically trained study personnel.

Baseline for analysis is set at day 14 reflecting completion of the allocated vaccinations. We will however also conduct the analysis from day 0-14. Participants can register a maximum of one infectious disease event per survey period (14 days).

A secondary analysis of association between influenza antibody level and subsequent risk of infection will be performed to test if high antibody titers correlate with risk of infection.

*Immunological outcomes (subgroup analyses):*

A random subset of participants (the first to accept) have extra blood samples taken for further immunological analyses.

1. Lymphocyte-dependent responses 7 days after influenza vaccination
2. The induction of innate immune memory 14- and 42-days post-randomization

For the lymphocyte analyses, 10 participants from groups 1-3 will have blood drawn on day 21, exactly 7 days after influenza vaccination. We will assess the effect of the different treatment combinations on the response to the influenza vaccine, examining activated

influenza antibody-secreting B-lymphocytes. Due to the different timing of the influenza vaccination, participants from group 4 are not part of this analysis.

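### Part A defines the doctor-visit component of the primary composite as infectious illness, measures it with a yes/no question on any new illness, and gives no rule linking the two.

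*SAP*

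**What the plan says.** Section 6.0 of Part A (Primary outcome) builds the composite from register data on hospital contacts, deaths and antibiotics, plus one self-reported component. That component, the doctor-identified infection, is "defined as newly onset infectious illness that has prompted the participant to seek medical attention" from a GP or on-call doctor.

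The Variables table repeats the requirement twice. The composite row reads "Death, hospitalization, antibiotic treatment, or visit to GP due to newly onset infectious disease. Composite outcome", and the component row reads "Infection identified by GP or on-call doctor".

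The measurement is described in one sentence: "Participants are asked in the questionnaires, if they have needed to see their GP or an on-call doctor due to newly onset illness" in the preceding 14 days, yes or no. The next sentence draws a consequence from it: "Thus, participants can only have one such event per survey period (14 days").

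Elsewhere the SAP does write classification rules for self-reported illness. Part A, section 6.0 (Secondary outcomes) has a symptom and diagnosis rule, for respiratory infection only. Part B, section 13.0 (Secondary outcomes) lists symptoms for any infection and adds "Having described an infectious disease as the self-estimated cause of illness", a free-text answer that medically trained staff classify. Neither rule is applied to the doctor component in Part A.

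**The concern.** The definition and the question cover different sets of visits. People aged 65 or over also see a doctor for new cardiac, musculoskeletal, neurological and other problems that are not infections. A participant with such a visit can truthfully answer yes, and Part A has no step that removes the answer.

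Two results are exposed. One is the primary composite. The other is the doctor component, which section 7.0 and Table 2 report with its own hazard ratio and where no register-based event dilutes the misclassification. If BCG does not affect non-infectious visits, counting them moves both hazard ratios toward 1.

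Reproducibility also suffers. Two analysts following this SAP could arrive at different primary event counts. The trial is single-blinded and analysed after it ends, so a filter chosen at that stage without written criteria would be an undocumented decision on the primary outcome.

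**Working it through.** **Inputs.** Control incidence 20%, relative reduction 25%, 945 per group and 1706 recruited, so 1706/2 = 853 per arm (all SAP Part A, section 3.0, Sample size). Two-sided 0.05 (section 4.0). Part A states no power; 80% is assumed, the value given in Part B. The non-infectious share is not in the SAP and is assumed throughout.

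**The plan's own figure.** With p1 = 0.20, p2 = 0.15, mean 0.175 and d = 0.05:

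n = [1.960·√(2·0.175·0.825) + 0.842·√(0.20·0.80 + 0.15·0.85)]² / 0.05² = 906 per group.

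The continuity correction (n/4)·[1 + √(1 + 4/(n·d))]² raises this to 945, which matches the SAP exactly. Power for 20% against 15%, without continuity correction, is 82% at 945 and 78% at 853. With the correction it is 80% and 76%. The figures below are without it.

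**Dilution, total control risk held at 20%.** Let s be the share of control-arm composite risk that is non-infectious and unaffected by BCG.

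- Unfiltered: p1 = 0.20, p2 = 0.20·[s + 0.75(1 − s)], so RR = 1 − 0.25(1 − s).
- Filtered to infections: p1 = 0.20(1 − s), p2 = 0.75·p1, so RR = 0.75 on fewer events.
- Power = Φ{[d − 1.960·√(2p̄(1 − p̄)/n)] / √[(p1(1 − p1) + p2(1 − p2))/n]}.

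| s | Unfiltered risks | RR | Power, 853 | Filtered risks | Power, 853 | Difference |
|---|---|---|---|---|---|---|
| 10% | 20% v 15.5% | 0.775 | 68% | 18% v 13.5% | 72% | 4 points |
| 20% | 20% v 16% | 0.80 | 58% | 16% v 12% | 66% | 9 points |
| 30% | 20% v 16.5% | 0.825 | 46% | 14% v 10.5% | 60% | 13 points |

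At 945 per arm the pairs are 73% v 77%, 62% v 71% and 50% v 64%. With the continuity correction the differences at 853 stay at about 4, 9 and 13 points.

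**Dilution, infections alone at 20%.** If the planned 20% is infections only and an independent non-infectious risk q is added, then p1 = 1 − 0.80(1 − q) and p2 = 1 − 0.85(1 − q). For q = 5% this gives 24.0% v 19.25%, RR 0.802 and power 66% at 853. For q = 10% it gives 28.0% v 23.5%, RR 0.839 and power 57%. Here a perfect filter would restore 20% v 15% and 78%.

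**Doctor component alone.** The same formula applies with that component's own share, which can be larger than the composite's. An assumed share of 50% would turn 0.75 into 1 − 0.25·0.5 = 0.875.

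**The case against.** A reader might infer that the SAP counts non-infectious visits as primary events. The text does not support that. Each time it defines this component it requires infection, and no sentence says that a yes for another reason is an event. The sentence on one event per survey period can be read as a cap that follows from asking once per 14 days. Section 3.0 says the questionnaires cover illness as well as medical contacts, so an analyst could filter the answers to fit the definition. This stands as far as intention goes. It does not supply the rule: with a filter, the symptoms, the causes and the classifier are unstated; without one, the definition is not met.

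A reader might also compare 68%, 58% or 46% with the 78% expected at 853 per arm and charge the whole drop to the missing rule. Those figures hold the total at 20%, so they also lower the true infection risk to 18%, 16% or 14%. Filtering would recover only 72%, 66% or 60%.

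Three further limits stand:

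- The shares apply to composite events, and nothing in the SAP supports any particular value. Section 7.0 (Missing data) says the primary outcome rests mostly on register data. A visit that falls within 14 days of a register event need not add a new one.
- The planned analysis is an Andersen-Gill model, not a comparison of two proportions.
- The Part B criteria were not written for doctor-attended illness and could lose a urinary or skin infection that has no listed symptom and no stated cause.

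**Conclusion.** The point holds as a mismatch between definition and measurement in a component of the primary outcome, with no rule in Part A to resolve it. It is not a declared decision to count non-infectious visits. Dilution follows only if the item is used as described and BCG leaves non-infectious visits unchanged.

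Its size cannot be calculated from the SAP. With 10% to 30% of a 20% control risk assumed non-infectious, the risk ratio moves from 0.75 to between 0.775 and 0.825, and the power attributable to the missing filter at 853 per arm is about 4 to 13 points. If the 20% refers to infections alone, added risks of 5% and 10% would cost about 11 and 21 points (78% to 66% and 57%). All these figures are indicative. Recruitment reached 1706 of the intended 1900, so there is little power to spare. The rule should be written before the primary outcome is coded.

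**What to change.** Add to section 6.0 of Part A that a yes to the doctor-visit item counts only when the same questionnaire also reports symptoms compatible with infection or an infectious cause. Criteria like those in Part B, section 13.0 can serve, extended so that non-respiratory infections such as urinary and skin infections are not lost. State who classifies, and that this is done blind to arm. Report the unfiltered version of the composite and of the doctor component as a sensitivity analysis.

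If the Part A questionnaires cannot support this, relabel the component as a visit for any new illness, align the Variables table with that, and add a sensitivity analysis of the composite without it.

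The cost is a short SAP amendment and recoding of questionnaire data already held. Somewhat fewer events will be counted, and the filter may miss some true infections; the unfiltered analysis shows how much depends on it.
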